5.4 Study Outcomes

The primary outcome will be 48-hour standing scale weight change (kg) from enrollment among the metolazone, intravenous chlorothiazide, and tolvaptan arms, using metolazone group as the comparator group for all other groups.

Secondary outcomes, using metolazone as the comparator group for each, will be:

- 48 hour net urine output (mls)
- mean change in serum creatinine, blood urea nitrogen, and eGFR at 24 hours, 48hours, and at hospital discharge
- mean change in diuretic efficiency at 24 and 48 hours from baseline value at enrollment
- mean change in serum potassium at 24 and 48 hours from baseline value at enrollment
- mean change in serum sodium at 24 hours, 48hrs, and at discharge from baseline value at enrollment
- cumulative dose of potassium (mEq) and magnesium (g) supplementation administered at 24 and 48 hours
- incidence of severe hypokalemia
- need for escalation in study-directed loop diuretic therapy at 24 and 48 hours
- addition of vasoactive or inotropic medication at 24 and 48 hours
- Treatment failure (definition below)
- Patient-scored congestion visual analog scale score at baseline, 24 and 48 hours (Appendix B)
- new cardiac arrhythmias (atrial and ventricular) during the study period
- receipt of inotropic therapy, dopamine, or nitroglycerin; requirement of ultrafiltration or hemodialysis during index hospitalization
- in-hospital mortality
- pharmacoeconomic analysis of the direct costs in each arm including the cost of:
 - study medication
 - additional non-trial protocol laboratory analysis cost related to monitoring of electrolytes
 - treatment of study medication related adverse effects (arrhythmias, hypotension, electrolyte repletion)
 - escalation of loop diuretic therapy doses
 - addition of additional therapies for suboptimal diuresis (inotropic therapy, vasodilators)
 - new initiation of renal replacement therapies (hemodialysis or ultrafiltration)
- Spot urinary electrolytes and diuretic urine concentration
- Pharmacokinetics and pharmacodynamics of the diuretics in the urine and blood
- Fractional excretion of sodium

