5.5 Study Definitions

- Urine output: Total urine volume (ml) from time of study enrollment to 48 hours
- Hypokalemia: Serum potassium value < 3.5mEq/L
- Severe Hypokalemia: Serum potassium value < 3.0mEq/L
- Hyponatremia: Serum sodium value < 135mEq/L

- Severe Hyponatremia: Serum sodium value < 130mEq/L and a decrease of 5mEq/L or more from enrollment serum sodium
- Overcorrection of serum sodium: increase in serum sodium from baseline by ≥ 12 mEq/L in 24 hours, increase in >8 mEq/L in 12 hours, or receipt of intravenous fluids because of symptoms of overcorrection of serum sodium regardless of the numerical rise
- Hypomagnesiemia: Serum magnesium value < 2mEq/L
- Diuretic efficiency = 24hr urine output/ 24hr Lasix equivalents in milligrams
- Weight: Standing weight on the same scale as used for baseline weight measurement
- New Atrial Arrhythmia: A “new” diagnosis of atrial arrhythmia (includes atrial fibrillation, atrial flutter, ectopic atrial tachycardia) lasting > 30 seconds OR any atrial arrhythmia which causes hemodynamic instability (MAP < 60 and requiring intervention)
- New Ventricular Arrhythmia: Ventricular tachycardia lasting longer than 30 seconds, or frequent non-sustained VT causing hemodynamic instability with MAP < 60 mmHg requiring intervention or > 1 intra-cardiac defibrillation or external cardiac defibrillation shock or ventricular fibrillation requiring defibrillation
- Hypotension: SBP < 85 for 2 repeated measurements within 30 minutes or lasting at least 30 minutes or symptomatic hypotension necessitating clinical intervention (defined as vasopressor support, intravenous fluid boluses, or initiation of inotropes)
- Treatment failure: Patients requiring additional non-study diuretic (spironolactone doses >75 mg/day, eplerenone > 75 mg/day, non-study thiazides (at a dose of metolazone 2.5mg or greater equivalence) or loop diuretics, or systemic acetazolamide (for diuretic indication), triamterene, or amiloride therapy) at any time during the 48-hour randomization period. These patients will be considered treatment failures for the purpose of analysis of the primary endpoint and all secondary endpoints.
- Patients whose cardiologist adds inotropic or vasodilator medications will not be considered treatment failures. Patients who require an increase in the loop diuretic regimen will also not be considered treatment failures.

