5.6 Study Outcome Timeline

Day 1: Baseline standing weight, BMP every 12 hours, urine collection, 20ml blood collection dyspnea score.

Day 2: 24 hour urine collection/quantification, BMP every 12 hours, 24 hour standing weight, 20ml blood collection, 24 hour dyspnea score, receipt of non-study diuretics, need of new inotropes or vasodilators

Day 3: 48 urine collection/quantification, 48 hour standing weight, 20ml blood collection, 48 hour dyspnea score, receipt of non-study diuretics, need of new inotropes or vasodilators.

End of study.

Day 30 (+/- 2 days): Telephone contact for the following events in past 30 days:

- ER visits and reason for visits
- Hospitalizations and reason for hospitalizations
- Serious adverse events

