8.0 Study Withdrawal/Discontinuation

A patient may withdraw at the study at anytime. The patient will inform the site investigator of their desire to withdraw. All study-based therapy will stop at this point, and the attending cardiologist will perform any further care. All study data collected to that time point will be included in the analysis. The withdrawal reason will be documented.

The site investigator will withdraw patients requiring therapy for overcorrection of serum sodium who experience any neurologic symptoms or who do not respond to intravenous D5W therapy within 6 hours. All patients will be followed per the study protocol through Day 30.

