9.3 Statistical Methods

We will utilize an intention-to-treat analysis for the primary outcome. We will also perform a per-protocol analysis for the primary outcome in patients completing the 48-hour treatment period without missing study doses. Metolazone will be the comparator arm, against which both chlorothiazide and tolvaptan treatment arms will be individually compared. Parametric continuous variables will be presented as mean (standard deviation) and non-parametric continuous variables will be presented as median (interquartile range). Nominal data will be presented as the number (percentage). We will employ a student's t test for the independent continuous primary outcome variable and other secondary outcomes using metolazone as the comparison group for both intravenous chlorothiazide and oral tolvaptan. For secondary outcomes, of which metolazone will again be the comparison group, fisher's exact test will be used for secondary outcomes that are nominal data. A two tailed p-value of less than or equal to 0.05 will be considered significant.

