Appendix A: Schedule of Study Assessments

	Screen	Baseline	12 hrs	24hrs	36 hrs	48 hrs	Day 30 (Phone Call)
Informed Consent	x						
Inclusion/Exclusion Criteria	x						
Screening electrolytes, renal function, liver function, pregnancy status if applicable	x						
Vital Signs	x	x	x	x	x	x	
Standing Weight		x		x		x	
Current Cardiovascular Medications		x		x		x	
Loop diuretic regimen evaluation	x	x		x		x	
BMP	x	x	x	x	x	x	
Biobank blood		x		x		x	
Biobank plasma		x		x		x	
Urine Collection	x	x	x	x	x	x	
Congestion Score Assessment		x		x		x	
Adverse Event Assessment				x		x	
Outcomes Assessment						x	x

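### The primary t test on 48-hour weight change cannot use a patient without a 48-hour weight, and the scheduled 24-hour weight that could help is left out

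*Combined protocol and SAP*

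**What the plan says.** Section 5.4 defines the endpoint: "The primary outcome will be 48-hour standing scale weight change (kg) from enrollment". Section 5.5 restricts what counts as a weight: "Weight: Standing weight on the same scale as used for baseline weight measurement".

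Section 9.3 sets the population, "We will utilize an intention-to-treat analysis for the primary outcome", and the method, "We will employ a student's t test for the independent continuous primary outcome variable", with chlorothiazide and tolvaptan each compared with metolazone. It adds a "per-protocol analysis for the primary outcome in patients completing the 48-hour treatment period without missing study doses".

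For a patient who withdraws, section 8.0 says: "All study data collected to that time point will be included in the analysis".

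Section 5.6 lists a "24 hour standing weight" on Day 2, and the "Standing Weight" row of Appendix A is marked at baseline, 24 hours and 48 hours. The 24-hour weight is not a listed outcome in section 5.4 and enters no analysis in section 9.3.

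The documents give no imputation, carry-forward rule, longitudinal model or missing-data sensitivity analysis. Section 5.5 says that treatment failures count as such in the analysis of the primary endpoint, but assigns them no value in kilograms. Section 9.1 sets 60 patients, 20 per arm, with no allowance for missing weights.

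**The concern.** A two-sample t test on 48-hour change needs a baseline and a 48-hour weight from each patient. Someone who withdraws, dies, or cannot be weighed standing on the same scale at 48 hours has no value to enter. As written, the test becomes an analysis of patients with a 48-hour weight. That sits poorly with intention-to-treat and with the section 8.0 statement on data collected before withdrawal. It also moves the intention-to-treat set towards the completers who form the per-protocol set, so comparing the two says less.

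Two things are at stake. Power falls with each missing weight, because the sample size has no reserve. And if the chance of a missing weight depends on response, and so differs between arms, the estimated difference is biased. The 24-hour weight carries information on both, at no cost in data collection.

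**Working it through.** **Inputs from the documents.** 20 per arm (9.1); SD 1.6 kg, difference 1.5 kg, type I error 0.05, power 82.3% (9.2); two-sided test (9.3).

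**Step 1: the plan's own figure.** With m patients observed per arm, the standard error is SE = 1.6 × √(2/m), the noncentrality is 1.5/SE, and power comes from the noncentral t distribution with 2m − 2 degrees of freedom. For m = 20, SE = 1.6 × √0.1 = 0.506 kg and the noncentrality is 2.965. With 38 degrees of freedom the power is 82.36%. The stated 82.3% reproduces, provided that all 20 per arm have a 48-hour weight.

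**Step 2: the same test with weights missing equally in both arms.**

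| Missing per arm | m | SE (kg) | Power |
|---|---|---|---|
| 0 | 20 | 0.506 | 82.4% |
| 1 | 19 | 0.519 | 80.3% |
| 2 | 18 | 0.533 | 78.0% |
| 3 | 17 | 0.549 | 75.5% |
| 4 | 16 | 0.566 | 72.8% |

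**Step 3: what the 24-hour weight recovers.** Let ρ be the correlation between 24- and 48-hour change. The documents do not give it; 0.5 to 0.9 is assumed. If every patient without a 48-hour weight has a 24-hour one, the variance of an arm mean is approximately 1.6² × [(1 − ρ²)/m + ρ²/20]. The effective number per arm is the inverse of the bracket. For m = 18 and ρ = 0.8 this is 1/(0.36/18 + 0.64/20) = 1/0.052 = 19.23, which gives 80.8% power. Over the range of ρ:

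| Missing per arm | t test | Using the 24-hour weight |
|---|---|---|
| 2 | 78.0% | 79.1% to 81.5% |
| 3 | 75.5% | 77.2% to 81.0% |
| 4 | 72.8% | 75.1% to 80.5% |

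**Step 4: bias if loss follows poor 24-hour response.** This is a simulation of two arms of 20. The assumptions are a true difference of 1.5 kg at 48 hours and 0.75 kg at 24 hours, SD 1.6 kg and 1.1 kg, ρ = 0.75, and a logistic probability of loss that rises as 24-hour weight loss falls.

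| Missing, better / worse arm | t test: difference, power | Using the 24-hour weight |
|---|---|---|
| about 3% / 5% | 1.47 kg, 80% | about 1.50 kg, 81% |
| about 7% / 13% | 1.43 kg, 76% | about 1.50 kg, 80% |
| about 15% / 25% | 1.39 kg, 69% | about 1.50 kg, 78% |

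The largest shift is 1.50 − 1.39 = 0.11 kg, about one fifth of the 0.506 kg standard error. Loss here depends only on the 24-hour change, which is the mechanism that the longitudinal model corrects. The last column is therefore a best case.

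**Step 5: bias without that mechanism.** If k of 20 patients in one arm are missing and their mean change differs by D kg from those observed, that arm's mean is off by (k/20) × D. With D = 2 kg (assumed), this is 0.2 kg for k = 2 and 0.4 kg for k = 4. The 24-hour weight need not remove such an error, so a sensitivity analysis is also needed.

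**The case against.** The strongest reply is that the documents show an unwritten missing-data policy, not a broken rule. Section 8.0 speaks of the analysis in general, not of the primary test, and section 5.4 has many 24-hour secondary outcomes to which a patient withdrawing after 24 hours can contribute. Section 9.3 never says that anyone is excluded. A reader might infer that the t test flatly contradicts two stated rules; the wording does not go that far. What stands is narrower: the named test cannot use these patients, and nothing named beside it can.

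Missing weights may also be few. The study lasts 48 hours in hospital (4.0, 6.0), and inability to perform standing weights is an exclusion at enrollment (3.0). Patients whom the investigator withdraws for sodium overcorrection stay in follow-up (8.0) and may still be weighed. A patient given a non-study diuretic is a treatment failure, but nothing says that the weight is not taken. This argument largely stands on size: at about 3% to 5% missing, the gain from the 24-hour weight is about one percentage point of power.

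A reader might also infer that the missing patients are the poor responders, and that the resulting bias favours the trial's own expectation of little difference in weight loss (2.0). The documents support neither step. The only investigator-initiated withdrawal they describe follows overcorrection of sodium (8.0), a risk that section 6.0 presents as particular to tolvaptan relative to the thiazides. That is not poor diuresis. With no true difference and about 14% missing per arm, the simulated t test gave a mean difference of 0.00 kg and rejected in 4.9% of trials.

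Finally, a longitudinal model does not by itself deliver intention-to-treat. Patients lost before 24 hours still contribute no post-dose weight. That objection is right, and the fix has to cover it.

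**Conclusion.** The point holds as an inexpensive improvement to the primary analysis. The t test in section 9.3 cannot use a patient without a 48-hour weight, no rule fills the gap, and a scheduled measurement that would help is unused.

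The power figures at a given number missing follow from the plan's own inputs: 82.3% is reached only with complete data, and falls to 72.8% with 4 missing per arm. How many will be missing is not stated, and for a 48-hour inpatient trial it may be few.

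The bias is conditional. A fall from 1.50 kg to about 1.47 to 1.39 kg rests on assumed missing rates of about 3% to 25% per arm, an assumed correlation, and loss driven by poor 24-hour response. Even then it is small beside a standard error of about 0.5 kg. The documents do not establish its direction, and they do not support a claim that it tilts the trial towards its expected answer.

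**What to change.** Make the primary analysis a repeated-measures model of weight change at 24 and 48 hours, with treatment, time, treatment-by-time, baseline weight, an unstructured covariance and a small-sample degrees-of-freedom correction such as Kenward-Roger. The two 48-hour contrasts with metolazone are primary. Keep the t test as a sensitivity analysis.

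In sections 8.0 and 9.3, also:

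- provide for the 48-hour weight to be obtained after study drug stops, where consent allows;
- state how patients with no post-dose weight, deaths and the treatment failures of section 5.5 enter the primary analysis;
- add a sensitivity analysis for weights not missing at random, for example by shifting the missing values over a stated range.

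The cost is plan wording and modest analysis work, with no new scheduled measurement. The downside is that the model relies on weights being missing at random given the 24-hour weight, which is why the last item is needed. The choice should be fixed before unblinding: with 20 per arm, a method chosen afterwards would leave the primary result open to challenge.

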9.0 Statistical Considerations

9.1 Sample Size

The study will have a sample size of 60 patients, equally allocated to the three study treatment groups.

9.2 Power Analysis

We have collaborated with Department of Biostatistics at Vanderbilt University Medical Center to employ the best statistical methods that allow our study to be realistic and achievable. Power calculations are difficult because of the lack of prospective trials comparing combination diuretic therapy and the numerous flaws in the methods of these previous studies. We will utilize change in weight as the primary outcome because weight change has been utilized as a primary efficacy outcome in landmark heart failure diuretic trials (CARRESS-HF¹⁹) and has less standard deviation than net urine output. In previous studies standard deviation of weight loss changes between groups varied with an approximate value of 1.6kg.^{14, 23} If the minimum clinically meaningful difference in the experimental and control means is 1.5kg, we will be able to reject the null hypothesis that the population means of the experimental and control groups are equal with 82.3% power. The Type I error probability associated with this test of this null hypothesis is 0.05.

9.3 Statistical Methods

We will utilize an intention-to-treat analysis for the primary outcome. We will also perform a per-protocol analysis for the primary outcome in patients completing the 48-hour treatment period without missing study doses. Metolazone will be the comparator arm, against which both chlorothiazide and tolvaptan treatment arms will be individually compared. Parametric continuous variables will be presented as mean (standard deviation) and non-parametric continuous variables will be presented as median (interquartile range). Nominal data will be presented as the number (percentage). We will employ a student's t test for the independent continuous primary outcome variable and other secondary outcomes using metolazone as the comparison group for both intravenous chlorothiazide and oral tolvaptan. For secondary outcomes, of which metolazone will again be the comparison group, fisher's exact test will be used for secondary outcomes that are nominal data. A two tailed p-value of less than or equal to 0.05 will be considered significant.

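### Cheap improvement, not an error: report each primary weight difference with a 95% CI read against 1.5 kg, and estimate it by pairwise ANCOVA on the baseline weight already collected

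*Combined protocol and SAP*

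**What the plan says.** Section 5.4 defines the endpoint: "The primary outcome will be 48-hour standing scale weight change (kg) from enrollment". Section 9.3 then names a Student's "t test for the independent continuous primary outcome variable and other secondary outcomes using metolazone as the comparison group", and adds: "Metolazone will be the comparator arm, against which both chlorothiazide and tolvaptan treatment arms will be individually compared". Results are shown as mean (SD), median (IQR) or counts, with significance declared at a two-tailed p of 0.05 or less. No covariate, regression model or confidence interval appears in the documents.

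Baseline weight is collected. Section 5.6 lists "Day 1: Baseline standing weight, BMP every 12 hours", and the "Standing Weight" row of Appendix A is ticked at baseline, 24 and 48 hours. The plan uses the baseline value only by subtracting it.

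Section 2.0 (Aim 1) states two expectations. Chlorothiazide should not produce a clinically meaningful increase in weight loss over metolazone, and tolvaptan should produce equal weight loss. Section 9.2 takes 1.5 kg as the smallest difference that matters clinically.

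**The concern.** Both expectations in Aim 1 are of no important difference. If they are right, the planned tests will usually be non-significant. A non-significant p-value does not separate a difference shown to be below 1.5 kg from a trial too imprecise to tell; an interval does. The two expectations also differ in shape. The chlorothiazide one is directional, so only the limit for greater chlorothiazide weight loss bears on it. The tolvaptan one is two-sided and needs both limits.

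Separately, a baseline value that is already measured goes unused as a predictor. If heavier patients tend to lose more (or less) weight in 48 hours, adjusting for baseline weight narrows the interval without new data or patients.

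**Working it through.** **Inputs.** 20 patients per arm (9.1); SD of weight change 1.6 kg, difference 1.5 kg and type I error 0.05 (9.2); two-sided testing (9.3). Section 9.2 gives the SD thus: "In previous studies standard deviation of weight loss changes between groups varied with an approximate value of 1.6kg". The correlation R between baseline weight and 48-hour weight change within an arm is not in the documents. It is assumed here over 0 to 0.5.

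**1. The plan's own figure.** SE = 1.6 × √(2/20) = 0.506 kg. Noncentrality = 1.5/0.506 = 2.96 on 38 df. Two-sided power is 82.4%, which agrees with the stated "the population means of the experimental and control groups are equal with 82.3% power".

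**2. Width of the unadjusted interval.** Half-width = 2.024 × 0.506 = 1.02 kg. Let D be observed weight loss in the experimental arm minus that in the metolazone arm.
- Tolvaptan (both limits): 1.5 kg is excluded when |D| < 1.50 − 1.02 = 0.48 kg.
- Chlorothiazide (upper limit only): a 1.5 kg increase is excluded when D < 0.48 kg, which includes every negative D.
- When |D| lies between 0.48 and 1.02 kg, the test is non-significant but the interval still includes a difference of 1.5 kg in one direction.

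**3. How often this matters.** In simulated trials with a true difference of 0 (20 per arm, SD 1.6 kg), about 95% of t tests are non-significant. About 65% of trials have a 95% CI that excludes 1.5 kg in both directions. The remaining 30% or so are non-significant without excluding it. The one-sided chlorothiazide condition is met in about 82% of trials.

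**4. Pairwise ANCOVA with baseline weight.** Residual SD = 1.6 × √(1 − R²). The variance is multiplied by 1 + 1/36 for chance baseline imbalance, and df = 37. At R = 0.3, for example, residual SD = 1.526 kg, SE = 1.526 × √(2/20) × √(37/36) = 0.489 kg, and half-width = 2.026 × 0.489 = 0.99 kg.

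| | t test | R = 0 | R = 0.2 | R = 0.3 | R = 0.5 |
|---|---|---|---|---|---|
| Power for 1.5 kg (formula) | 82.4% | 81.3% | 82.8% | 84.7% | 90.8% |
| 95% CI half-width, kg (formula) | 1.02 | 1.04 | 1.02 | 0.99 | 0.90 |
| Chance that the CI excludes 1.5 kg both ways, true difference 0 (simulated) | about 65% | about 62% | about 66% | about 69% | about 82% |

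Power breaks even with the t test at R of about 0.17. Simulated power agrees with the formula, and simulated type I error stays near 5% for both methods (4.7% to 5.2%).

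**The case against.** The plan has no defect to cure. It names the test, comparator, sidedness and alpha, and it powers that same test. All of that stands. A reader might infer that the t test is invalid or the power wrong; the documents support neither, because the test is sound and the figure reproduces.

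The gain from ANCOVA depends on an R that the documents do not supply. The outcome is already a change from baseline, and nothing in the text says that baseline body weight predicts 48-hour loss. That also stands. Below about 0.17 the adjustment loses slightly, and at 0.3 the gain is about 2 points of power and 0.03 kg of half-width. A reader might take the R = 0.5 column as a promised gain; it is only the top of an assumed range.

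A reader might also apply the 0.48 kg limit in both directions to both drugs. Aim 1 does not support that for chlorothiazide, where only an increase is at issue. Nor do the documents set up a formal equivalence test. If they did, the usual 5% procedure would use a 90% interval (half-width 0.85 kg, limit 0.65 kg), so reading a 95% interval is the stricter course.

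Finally, an interval could be worked out later from the reported means, SDs and sample sizes. True, but committing to it in advance ties the conclusion to the plan's own 1.5 kg. The case for the interval also stands without ANCOVA, and is the firmer half of the proposal.

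**Conclusion.** An optional, low-cost improvement. The interval is worth planning whatever R is: on the plan's own SD and sample size, roughly 3 in 10 trials with no true difference would be non-significant yet leave 1.5 kg open in one direction, and the planned p-value would not show it. The covariate is a modest bet with a bounded loss and a possibly larger gain, which is small unless R is at least moderate. These sizes rest on SD 1.6 kg in each arm, 20 analysed patients per arm, normally distributed outcomes and the assumed values of R. A different observed SD would move the 0.48 kg limit.

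**What to change.** Amend section 9.3 before unblinding:

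- Estimate each primary contrast (chlorothiazide versus metolazone, tolvaptan versus metolazone) by a prespecified ANCOVA of 48-hour weight change on arm and baseline standing weight. Fit each pair of arms separately, in keeping with the plan's individual comparisons. Use the same baseline weight that enters the change.
- Report each adjusted difference with its 95% CI and read it against 1.5 kg. For chlorothiazide use only the limit for greater chlorothiazide weight loss; for tolvaptan use both limits.

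If the team prefers to keep the t test as primary, adding the 95% CI alone still secures the firmer half.

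Cost: SAP wording only, with no new data, patients or change in sample size. If R is near 0, the covariate costs about 1 point of power (82.4% to 81.3%) and about 2 points of the chance of excluding 1.5 kg both ways (about 65% to 62%).
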